- A) We will ask participants to return for 2 visits in which we will administer methacholine concurrently with varying levels of PEEP (using PEEP to prevent bronchoconstriction).
- B) Subject will return for another 2 visits in which we will determine the effects of PEEP subsequent to methacholine challenge (using PEEP to reverse bronchoconstriction).

The reason to test both short-term time points is to assess:

- A) whether PEEP has any value as an intervention that will prevent the immediate development of bronchoconstriction (i.e. bronchoprotection, analogous to using rescue therapy prior to exercise to prevent bronchoconstriction), and
- B) if PEEP will reverse established bronchoconstriction (i.e. bronchodilation, as a form of rescue therapy after onset of symptoms).

These studies will be completed over 5 visits. If necessary, participants may be asked to return for an additional visit if some of the lung function tests were not completed at the regularly scheduled visits, if the lung function testing was completed, but did not produce consistent and accurate results, or if there is a longer than expected gap between study visits, which creates a need to calculate a new PC₂₀ dose for the participant through an additional methacholine challenge.

Procedures: Describe all procedures (sequentially) to which human participants will be subjected. Identify all procedures that are considered experimental and/or procedures performed exclusively for research purposes. Describe the types, frequency and duration of tests, study visits, interviews, questionnaires, etc. Include required screening procedures performed before enrollment and while on study. Please provide in table, list or outline format for ease of review. (describe and attach all instruments)

Note: A clinical research protocol may involve interventions that are strictly experimental or it may involve some aspect of research (e.g., randomization among standard treatments for collection and analysis of routine clinical data for research purposes). It is important for this section to distinguish between interventions that are experimental and/or carried out for research purposes versus those procedures that are considered standard therapy. In addition, routine procedures performed solely for research purposes (e.g., additional diagnostic/follow-up tests) should be identified.

All procedures will be performed exclusively for research purposes.

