- Baseline Medical History: we will obtain a baseline medical history and record all medications
- Baseline anthropometrics (BMI, waist and hip circumference, as well as temperature and blood pressure)
- Asthma Questionnaires: participants will complete a validated questionnaire to assess asthma control.¹⁶
- Berlin Sleep Questionnaire (modified version)
- Blood draw: We will draw 10 cc of blood; this will go to the UVMMLC laboratory for measurement of complete blood count and differential, and IgE levels (these are used as measures of allergic status). IgE will not be repeated if tested previously.

- Blood draw: We will draw 16cc of blood, this will go to [name] UVM laboratory for measurement of serum biomarkers (used to detect circulating anti-inflammatory markers)
 - Subjects consenting to store leftover blood samples and data for future research on asthma and obesity will have sample stored in a bio-repository under CHRMS: 16-636.
- Spirometry without bronchodilator will be performed per standard clinical protocol.
- Urine pregnancy test will be performed at all visits.
- Lung Volumes will be measured per standard clinical protocol (by plethysmography).
- Methacholine challenge test (conventional): this will be performed per standard clinical protocol. Participants will inhale increasing doses of methacholine to identify the concentration of methacholine producing a 20% decrease in FEV₁ or FVC (the PC₂₀ dose); this concentration will be used in the subsequent single dose methacholine challenge testing.
- Chest CT: A chest CT will be performed with images at different lung volumes, and with PEEP at a setting of 10 cmH₂O, to assess changes in airway diameter during breathing (if participant has not had this performed previously as part of protocol 15-327 or protocol 16-061).
- Single breath nitrogen wash out: the participant will take a single deep breath of 100% oxygen, and then exhale through a one way valve. (if participant has not had this performed previously as part of protocol 15-327 or protocol 16-061).
- Multiple breath nitrogen wash out: the participants will breathe 100% oxygen for approximately 7 minutes (normal tidal breathing). (if participant has not had this performed previously as part of protocol 15-327 or protocol 16-061).

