- Single dose methacholine challenge test at PEEP 0 or PEEP 10 with forced oscillation: The experimental protocol will consist of having the subject breathe a fixed concentration of methacholine aerosol for four and a half minutes; we will use the dose of methacholine that produces a 20% fall in FEV₁. We will measure airway impedance by the forced oscillation technique before, during and after the inhalation of methacholine. Subjects breathe, taking normal breaths, through a conventional plastic mouthpiece attached to a specialized apparatus that measures respiratory impedance by pressure changes related to a variable airflow during normal breathing.

Study Visits:

	Visit 1	Visit 2	Visit 3	Visit 4	Visit 5
Baseline history	*				
IgE level / CBC with differential	*				
Serum Biomarker	*				
Pregnancy Test ¹	*	*	*	*	*
Asthma Control Questionnaire	*	*	*	*	*
Berlin Sleep Questionnaire	*				
Conventional methacholine	*				
Lung Volumes	*				
SBNW ²	*				
MBNW ²	*				
Training for CT breathing ²	*	*			
CT imaging ^{2,3}		*			
PEEP + methacholine together		*	*		

Methacholine prior to PEEP				*	*
PEEP level (cmH ₂ O)		0	10	0	10

¹For women of child-bearing potential

²Participants who have not previously completed these procedures as part of a related research protocol only.

³ CT imaging may be performed at any of visits 2-5, at convenience of participant

Study Visits:

There will be five regularly scheduled study visits, with some participants asked to complete a screening visit, as follows:

*Screening Visit: Participants who have not had a serum IgE level drawn/results are not available will be asked to attend a screening visit. The research staff will provide participants with full details of the study. Participants who sign a consent form will have blood drawn for measurement of IgE and Complete blood count with differential (assesses allergy, and required for eligibility assessment), and for serum anti-inflammatory biomarkers. In addition, the eligibility criteria for the study will be reviewed with the participants, which may involve a height and weight measured to test for BMI eligibility.

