Visit 1: This visit will take approximately 3 hours. The research staff will provide participants with full details of the study. Participants who sign a consent form will undergo the following procedures/ assessments. Past medical history, asthma control questionnaire, Berlin Sleep Questionnaire, urine pregnancy test, measurement of height, weight, blood pressure, waist and hip circumference, as well as temperature. Eligible participants will undergo spirometry and lung volumes measurements. Participants who have not previously had the following tests will undergo a single-breath (SBNW) and multi-breath (MBNW) nitrogen (N₂) washout methods to assess functional residual capacity (FRC), closing volume, closing capacity, lung clearance index (number of FRC turnovers required to reduce N₂ concentration to 1/40 of its initial value), and lung heterogeneity (reflected in the washout parameters Sacin and Scond).

Participants will undergo a standard methacholine challenge for measurement of PC₂₀, a standard measurement of airway reactivity. Using the medical records we will screen for methacholine challenge results performed in the past two weeks.

Participants will also have blood drawn at visit 1, which will go to [name] UVM laboratory for measurement of serum biomarkers. If this blood draw cannot happen at visit 1 for logistical reasons, then it may be performed at visits 2-5.

Visits 2-5 will be conducted in random order using a schema provided by the biometry facility at the University of Vermont.

Visits 2 & 3: Participants will be questioned about their interim history to asses for adverse events and will be asked to complete the asthma control questionnaire. In addition, participants will undergo a methcholine challenge, while we continuously measure their lung function by forced oscillation.

We will administer a single dose of methacholine (as determined by their PC₂₀ dose, the dose of methacholine required to produce a 20% decreased in FEV1), and measure respiratory system impedance with the forced oscillation system while concurrently applying either PEEP 0 or PEEP 10.

Visit 4 & 5: Participants will be questioned about their interim history to assess for adverse events, and will be asked to complete the asthma control questionnaire. In addition, participants will undergo a methcholine challenge, while we continuously measure their lung function by forced oscillation.

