We will administer a single dose of methacholine (as determined by their PC₂₀ dose, the dose of methacholine required to produce a 20% decreased in FEV1), and measure respiratory system impedance with the forced oscillation system, *after* the single dose of methacholine, we will apply either PEEP 0 or PEEP 10.

Participants who have not had a chest CT as part of protocol 15-327 will undergo a protocolized non-contrast chest CT. Images will be taken at full inspiration, resting expiration (FRC), full expiration (residual volume), and resting expiration with PEEP10cmH₂O. Images will be recorded using standardized procedures, and analyzed using commercially available software for quantification of airway diameter, airway thickness, and lung attenuation at standardized locations in both lung fields. These measurements will allow us to directly quantify changes in the large airways (diameter and wall thickness), and also airway trapping (degree of attenuation) through the normal respiratory cycle.

Additional Visit: Some participants may be asked to return for an additional visit if some of the lung function tests were not completed at the regularly scheduled visits, if the lung function testing was completed, but did not produce consistent and accurate results, or if there is a longer than expected gap between study visits, which creates the need to calculate a new PC₂₀ dose with an additional methacholine challenge.

This additional visit may involve spirometry, lung volume measurements, single-breath nitrogen washout, multiple-breath nitrogen washout, a methacholine challenge, or the forced oscillation procedure with a single dose of methacholine, depending on the need for the specific participant.

If methacholine is needed during the additional visit, the participant’s blood pressure will be assessed. In addition, women of childbearing potential will be required to undergo a urine pregnancy test prior to methacholine testing.

For research involving survey, questionnaires, etc.: Describe the setting and the mode of administering the instrument and the provisions for maintaining privacy and confidentiality. Include the duration, intervals of administration, and overall length of participation. (describe and attach all instruments)

Not applicable

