Baseline medical and asthma control questionnaires will take 5- 10 minutes to complete, will be completed at the Medical Office Building, in a private office. Questionnaires are in paper format, and will be completed by the participant.

Statistical Considerations: Delineate the precise outcomes to be measured and analyzed. Describe how these results will be measured and statistically analyzed. Delineate methods used to estimate the required number of subjects. Describe power calculations if the study involves comparisons. Perform this analysis on each of the primary and secondary objectives, if possible.

We will compare changes in respiratory system impedance across the 2 levels of PEEP for participants being exposed to methacholine prior to PEEP (visit 4-5) and methacholine simultaneously with PEEP (visits 2-3), separately.

We will also measure symptom scores using the Borg scale; symptom scores in the obese are related to lung reactance, and we anticipate that symptom scores will be decreased by the PEEP intervention and that this will correlate with decreases in measures of impedance.

The primary statistical analysis will be to compare changes in measures of impedance at PEEP 0 versus 10 cmH₂O using paired t-tests. If normal distribution assumptions are not met, variables will be appropriately transformed. We will compare data from visits 2-3, and visits 4-5 as separate experiments, as they address different scientific questions. We will also compare symptom scores (Borg scale) and, FRC at the two different levels of PEEP.

Power Analysis: Based on the preliminary data shown in Figs. 10 & 11 obtained with a PEEP of 10 cmH₂O, we anticipate that a PEEP of 10 cmH₂O will lead to a 50% attenuation in the increase in resistance in response to methacholine compared to the increase in resistance at PEEP 0, which will be our primary outcome of interest. From our prior work using a commercially available forced oscillation system in obese asthmatics,

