we anticipate that the baseline resistance of the respiratory system at a frequency of 5 Hz will be 7.02 ± 1.80 cmH₂O.s/L, and that this will increase to 10.50 ± 2.20 cmH₂O.s/L with a PC₁₀ dose of methacholine at PEEP = 0. Examination of the change in resistance in response to methacholine for PEEP = 0 compared to PEEP = 10 using a paired t-test with a 2.5% Type I error level and $r = 0.50$ within subject correlation indicates that a sample size of $n = 10$ LONA subjects will provide 99% power to detect the postulated within subject change. An independent comparison using a 2.5% Type I error level for the change in resistance prior to methacholine using the smaller effect sizes would require a sample size of $n = 15$ to achieve a 78% power. An adjusted 5% Type I error level was used to compensate for the two separate comparisons conducted for testing the resistance changes. We will increase this to 20 participants to allow for potential drop-outs and any technical difficulties participants experience with completing any of the study visits.

Confidentiality Measures and Secure Storage of Data or Tissue: Describe how the data/tissue will be collected. Will there be identifiers or will the data/tissue be coded? Describe where the data/tissue will be stored and how it will be secured. Describe who will have access to the data/tissue or the codes. If subject data/tissues with identifiers will be released, specify to whom. Describe what will happen to the data/tissues when the research has been completed.

Not Applicable

- Research material obtained from participants will include results of lung function testing, and medical history obtained from direct patient interview.
- People having access to protected data will be the investigators participating in this study and appropriate regulatory authorities.
- Documents containing identifiable information will be kept in a locked file cabinet at the Vermont Lung Center. All participants will be assigned a unique study ID, which be kept in this locked file cabinet. Study specimens will be labeled with the study ID, and not identifiable information. Our study database will be password protected, and participants will be identified in the database only by their unique participants ID.
- Optional Leftover blood samples and data for future research on asthma and obesity will be stored frozen in [name] UVM laboratory bio-repository (CHRMS: 16-636). The samples will be identified with the unique study ID and date only.

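### Does randomising visits 2-5 as one set, with plain paired t-tests and no visit-order term, weaken the two PEEP comparisons?

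*Combined protocol and SAP*

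**What the plan says.** Under Study Visits: "Visits 2-5 will be conducted in random order using a schema provided by the biometry facility at the University of Vermont". The schema is not described further.

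Statistical Considerations plans to "compare changes in measures of impedance at PEEP 0 versus 10 cmH₂O using paired t-tests", and adds: "We will compare data from visits 2-3, and visits 4-5 as separate experiments, as they address different scientific questions". No period, sequence or visit-order term is named.

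The Power Analysis gives 78% power at n = 15 and raises enrolment to 20 to "allow for potential drop-outs and any technical difficulties participants experience with completing any of the study visits".

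On the methacholine concentration, Procedures takes the value found at the conventional challenge and says "this concentration will be used in the subsequent single dose methacholine challenge testing". The single-dose test is described as "having the subject breathe a fixed concentration of methacholine aerosol for four and a half minutes". Study Design and the Additional Visit paragraph allow for "a longer than expected gap between study visits, which creates a need to calculate a new PC₂₀ dose for the participant".

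**The concern.** Four visits are randomised as one set, but two pairs are analysed. If every order is allowed, the PEEP 0 and PEEP 10 visits of one experiment can be separated by visits of the other, and by chance one PEEP level may come first more often. If the response to methacholine changes over the series of visits, that change enters the paired differences as noise, and a plain paired t-test does not remove it. In a study of 20 people, lost precision matters.

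A second strand concerns concentration. If a new PC₂₀ is calculated between the two visits of a pair, they may use different concentrations. The statistical section does not say what happens to such a pair, so the decision could in principle be made after the results are seen.

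**Working it through.** **Inputs (Statistical Considerations and Power Analysis).** Resistance 7.02 (SD 1.80) before and 10.50 (SD 2.20) after methacholine at PEEP 0; 50% attenuation; within-subject correlation 0.50; Type I error 2.5%, taken as two-sided.

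**The plan's own figure.**
- Rise: 10.50 − 7.02 = 3.48. Attenuation: 0.5 × 3.48 = 1.74.
- SD of the paired difference: √(1.80² + 2.20² − 2 × 0.5 × 1.80 × 2.20) = √4.12 = 2.03.
- Noncentral t: n = 15 gives 78.1% (stated 78%); n = 20 gives 90.9%.

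**What free order means.** Assume all 24 orders are equally likely (not stated). The two visits of a pair are then one, two or three positions apart with probability 1/2, 1/3 and 1/6. The mean squared distance is 1/2 × 1 + 1/3 × 4 + 1/6 × 9 = 3.33, against 1 if pairs are always consecutive. The signed distance averages zero, so additive drift does not shift the estimate. With a drift of d per visit, the variance of a paired difference becomes 4.12 + 3.33d² under free order and 4.12 + d² if blocked.

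**Effect of an assumed common drift.** Simulated power of the plain paired t-test:

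| Drift per visit (cmH₂O.s/L) | n = 15 free | n = 15 blocked | n = 20 free | n = 20 blocked |
|---|---|---|---|---|
| 0 | 78% | 78% | 91% | 91% |
| 0.25 | 76% | 77% | 89% | 90% |
| 0.5 | 70% | 75% | 85% | 89% |
| 1.0 | 50% | 68% | 66% | 83% |

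Type I error under free order is about 2.5% in every row. A drift of 0.5 per visit accumulates over three steps to 1.5, or 1.5/3.48 = 43% of the rise; a drift of 1.0 gives 86%. The outcome is a change in impedance, so a drift in resting resistance cancels. Only a drift in the response to methacholine counts.

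**Adding an order term under free order.** With no drift, a first/second-visit term lowers power from 78.1% to 74.0% at n = 15 and from 90.9% to 88.7% at n = 20. With a drift of 0.5 it raises power from 70% to 72% and from 85% to 88%. It is not a clear gain.

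**Blocking and carry-over.** Suppose a PEEP 10 visit adds L to the next visit's response.
- Free order: a PEEP 0 visit directly follows a PEEP 10 visit with probability 1/2, and a PEEP 10 visit directly follows the other PEEP 10 visit with probability 1/4. The PEEP 10 minus PEEP 0 difference shifts by L(1/4 − 1/2) = −L/4.
- Blocked order: the probabilities are 5/8 and 1/8, so the shift is L(1/8 − 5/8) = −L/2.

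With an assumed L of 1.0 and n = 20, simulated Type I error is about 4% under free order and 11% if blocked.

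**Early stopping.** Assume stops are spread evenly over the four gaps between the five visits. The expected number of complete pairs per stopper is (0 + 0 + 0.33 + 1)/4 = 0.33 under free order and (0 + 0 + 1 + 1)/4 = 0.50 if blocked. If 5 of 20 stop, each experiment keeps 15 + 5 × 0.33/2 = 15.8 against 15 + 5 × 0.50/2 = 16.3 pairs. Power is 80.9% against 82.2%.

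**Pairs at two concentrations.** Random order makes it a matter of chance which PEEP level gets the new concentration, so the shift is taken to have a random sign. With 4 of 20 pairs affected by an assumed shift of 0.87, 1.74 or 3.48, keeping all pairs gives 90%, 86% or 72% power and excluding them gives 82%, 81% or 81%. Type I error with all pairs kept is 2.3–2.5%.

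**The case for a change.** The strongest case for a change is that it would be cheap and that part of it needs no drift assumption. Describing the schema takes one sentence, and a written rule for mixed-concentration pairs would remove a choice from the analyst. The slack between 15 and 20 participants is already assigned to drop-outs and technical difficulties, so it should not also be spent on visit-order noise. At the larger drifts the loss is real.

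Some of this stands. The documents do not say whether the schema blocks or balances, and they give no rule for a mixed-concentration pair. But the protocol leaves the order to a biometry facility, and silence about the schema's content is not evidence that it lacks structure. The plan as written also has a natural reading for mixed pairs: every completed pair enters the paired t-test. That is the better choice in the figures above unless the shift is large. The recalculation provision reads as an exception to the carried-forward concentration, and the fixed concentration over four and a half minutes describes a single challenge, so these sections need not conflict.

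The attrition argument is worth about one power point, and the Additional Visit provision can rescue some incomplete pairs.

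**Conclusion.** No change to the plan is needed. Randomising the visit order protects the paired t-test against additive time effects, and Type I error stays at about 2.5%. What remains is a possible loss of precision: about 2 power points at the planned n = 20 for a drift of 0.25 cmH₂O.s/L per visit, about 6 points for 0.5, and more only if the methacholine response moves by most of its expected size over four visits. The protocol gives no sign of such a drift.

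The remedies are not clear improvements. Under free order an order term costs about 4 points at n = 15 when there is no drift. Blocking protects against drift but doubles the shift from any carry-over, and the protocol documents neither. The schema detail and the handling of mixed-concentration pairs are gaps that a competent analyst fills without affecting validity.

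This rests on equally likely orders, assumed values for drift, carry-over, stopping and concentration shifts, and the plan's SDs and correlation. The statement that validity holds covers additive drift; carry-over is the exception, and there free order is the less exposed of the two designs.

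### Does the planned FRC comparison between PEEP levels lack a usable measurement, and does CT on a challenge day threaten the impedance contrast?

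*Combined protocol and SAP*

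**What the plan says.** Statistical Considerations makes changes in impedance at PEEP 0 versus PEEP 10 the primary analysis, by paired t-test, with visits 2-3 and visits 4-5 treated as separate experiments. It then adds: "We will also compare symptom scores (Borg scale) and, FRC at the two different levels of PEEP".

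The possible sources of FRC in the schedule are these:

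- **Plethysmography and nitrogen washout.** Both are marked at visit 1 only, where the table's PEEP row is blank. The Visit 1 text describes "washout methods to assess functional residual capacity (FRC), closing volume, closing capacity" and does not mention PEEP.
- **Chest CT.** The Study Visits text says "Images will be taken at full inspiration, resting expiration (FRC), full expiration (residual volume), and resting expiration with PEEP10cmH₂O". The read-outs it lists are airway diameter, airway thickness and lung attenuation. Lung volume is not among them.

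The Study Visits table marks CT at visit 2, where the PEEP row reads 0. It marks "Training for CT breathing" at visits 1 and 2. Footnote 3 loosens the CT timing: "CT imaging may be performed at any of visits 2-5, at convenience of participant". The text also says "Visits 2-5 will be conducted in random order", and describes visits 2 and 3 as applying either PEEP level. The Procedures list exempts people from CT "if participant has not had this performed previously as part of protocol 15-327 or protocol 16-061". The later CT paragraph names only 15-327.

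**The concern.** A comparison is promised without a stated measurement. The named FRC tests are done without PEEP, and the one paired source sits on a methacholine day with no order given. Either order seems to cost something.

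- **Scan after the challenge.** Both resting-expiration images follow methacholine, and possibly a bronchodilator, so they no longer describe the undisturbed effect of PEEP on lung volume.
- **Scan before the challenge.** The participant takes a full inspiration and PEEP 10 shortly before an impedance challenge. Study Design describes the effect tested at visits 2-3 as "bronchoprotection, analogous to using rescue therapy prior to exercise to prevent bronchoconstriction". If some of that protection outlasted the PEEP, the rise at a PEEP 0 visit would be blunted and the contrast with PEEP 10 would shrink. If visit numbers label conditions, the table's CT mark falls on the PEEP 0 control of the visits 2-3 experiment and not on its pair, and randomising visit order would not balance that.

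At stake would be an uninterpretable FRC comparison and, on the second route, a primary contrast biased towards no effect.

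**Working it through.** **1. Is there a usable FRC pair?** Visits 2-5 list no FRC test at a stated PEEP level. CT is allowed on 4 visits, all 4 include methacholine, and no sentence gives the order. But one CT session takes resting expiration both without PEEP and at PEEP 10, so the pair lies within the session and that visit's assigned PEEP level is irrelevant to it. A scan before the day's methacholine is clear of that day's challenge. A scan from a related protocol may be clear too: nothing places those scans on a challenge day of this trial, although the documents do not say whether they include a PEEP 10 image.

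**2. The plan's own power figure.** Inputs from Power Analysis: resistance 7.02 ± 1.80 at baseline and 10.50 ± 2.20 after methacholine at PEEP 0, r = 0.50, 50% attenuation, 2.5% type I error (taken as two-sided).

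- Rise at PEEP 0: 10.50 − 7.02 = 3.48. Contrast at 50% attenuation: 3.48 × 0.5 = 1.74.
- SD: √(1.80² + 2.20² − 2 × 0.50 × 1.80 × 2.20) = √4.12 = 2.03. Standardised contrast: 1.74 / 2.03 = 0.857.
- Paired t-test, noncentral t: power 78.1% at n = 15, which matches the stated 78%, and 90.9% at n = 20.

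**3. Adding an assumed carry-over.** Let s be the share of the PEEP effect that reaches the PEEP 0 challenge, averaged over participants. The contrast becomes 1.74 × (1 − s). The documents give no value for s.

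| s | contrast | power, n = 15 | power, n = 20 |
|---|---|---|---|
| 0 | 1.74 | 78% | 91% |
| 5% | 1.65 | 73% | 88% |
| 6.25% | 1.63 | 72% | 87% |
| 10% | 1.57 | 68% | 84% |
| 25% | 1.31 | 51% | 67% |
| 50% | 0.87 | 23% | 33% |

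**4. What a given s requires.** s is the fraction of participants scanned before the relevant PEEP 0 challenge, times the share of effect that persists in them. Suppose nobody was scanned earlier, CT is spread evenly over four visits, and half the scans precede the challenge. Then 1/4 × 1/2 = 1/8 are exposed. If half the effect persists, s = 1/8 × 1/2 = 6.25%. Reaching s = 50% would need, for example, every participant scanned before that challenge with half the effect persisting. If the scan follows the readings, or was done under a related protocol, s is 0.

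**5. How far to trust the table.** The SD of 2.03 describes a baseline-to-methacholine change at one visit. Using it for the difference between two such rises implies equal SDs and a correlation of 0.5 between the rises, because 2.03 × √(2 × (1 − 0.5)) = 2.03. With correlation 0.3 or 0.7 instead, the SD is 2.40 or 1.57, and power at n = 15 with no carry-over is 62% or 95%. That uncertainty exceeds the effect of s = 6.25%.

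**6. The CT exemption.** Footnote 2 of the Study Visits table already limits CT to people who have not had it under a related research protocol, without naming one. That agrees with the Procedures list. The paragraph naming only 15-327 is the outlier.

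**The case for a change.** The strongest case for a change is that the form asks for outcomes to be stated precisely, and FRC is not: no method is named, and lung volume is missing from the CT read-outs. Leaving scan timing to the participant's convenience also leaves a bias route open in a trial of 20 people. If all were scanned at the table's listed visit, before a PEEP 0 challenge, s would equal the persisting share itself, and 25% would take power at n = 20 from 91% to 67%. Closing the route looks cheap: at most 20 extra visits at $50 each, or $1,000, plus mileage.

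The missing detail stands, and the bias route cannot be excluded. The step from there to an amendment does not hold. The bronchoprotection wording concerns PEEP given together with methacholine, and the Purpose section's rationale is that PEEP keeps airways open. Neither says that an effect outlasts the pressure. The remedies also cost something. Scanning after the readings spoils the FRC pair that the change is meant to protect. A separate day asks up to 20 people for another trip, and the additional visit as now described does not list CT.

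The Borg gap is of the same kind. Its visits can be inferred, and a reading at a common time with the assigned PEEP level applied is the natural choice.

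**Conclusion.** No change to the plan is needed. The FRC source, the order of scan and challenge, and the minute of the Borg reading are details that analysts can fill sensibly. For FRC the evident choice is resting-expiration lung volume with and without PEEP 10 from one CT session, read as a check that PEEP raises lung volume. The CT exemption mismatch is a clerical slip that footnote 2 resolves. Where to place CT is a fair trade-off between a clean scan, an unencumbered challenge and the number of trips.

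The missing FRC and Borg detail does not by itself affect the primary impedance analysis. Carry-over could, but its size is not known from the documents. In the illustration above it costs about 4 points of power at n = 20 (91% to 87%) and 6 at n = 15 (78% to 72%). The larger losses need most participants scanned before the relevant PEEP 0 challenge and a substantial lasting effect. This conclusion rests on there being no documented effect of PEEP after it is removed; evidence of one would reopen the question of scan order.
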